3.2 General study level definitions

3.2.1 Analysis time points

3.2.1.1 Relative day

- The relative day will be included in some listings and will be calculated as follows. The way that relative day is calculated depends on when the given event occurs relative to the date of first IMP administration. If the event start (stop) date occurred on or after the first dose of study drug administration, but prior to the study drug stop date, relative day is calculated as start (stop) date of the event minus first dose date of study drug dose + 1.

Relative day 1 is the date of first study drug administration.

- If the event start (stop) date occurred after the last dose of study drug administration, the relative day to the most recent study drug dose is calculated as start (stop) date of the event minus most recent study drug dose date. The relative day in this situation should be preceded by a '+'.
- If the event start (stop) date occurred before the first dose of study drug administration, the relative day is calculated as start (stop) date of the event minus first dose date of study drug dose. The relative day in this situation should be preceded by a '-'.

Relative day will only be computed for fully completed dates and will be left blank for partial dates.

For AEs, relative days for start and stop dates will be calculated as the number of days since the first IMP administration.

For events occurring after Week 16 in study participants who have switched from placebo to bimekizumab, an additional relative day will be calculated using the same rules as above but

based on the date of first injection of bimekizumab. This additional relative day will be provided in listings for concomitant medications and safety data.

For non-treatment emergent AEs, relative day of onset will be negative if the event started and stopped before the first dose. A complete date must be established in order to correctly identify the AEs. Section 4.2.2 describes imputation rules in case of missing data for AEs.

3.2.1.2 End date of the Treatment Period

The end of the Treatment Period will be either the date of Week 52 visit (Visit 17) for study participants completing the Treatment Period, or the date of the early termination (ET) visit for study participants who discontinued early during the Treatment Period.

Note that study participants who previously discontinued IMP and are continuing for all scheduled visits through Week 52 will also be considered as having completed the Treatment Period.

If a study participant does not have a Week 52/ET visit, then either the date of the last scheduled or unscheduled visit during the Treatment Period or the date of last known dose of study drug during the Treatment Period, whichever is later, will define the end date of the Treatment Period.

3.2.2 Study periods

3.2.2.1 Study periods for safety and efficacy data

Based on the specific requirements of safety analyses and efficacy analyses, two concepts of the definition of periods need to be considered for the study, which will be defined in detail in the sections below.

3.2.2.1.1 Study periods for safety data

The following study periods are defined for the classification of safety data by study period:

- Pre-treatment Period (Screening Period): Starts at the time of the informed consent date and ends prior to the day and time of the first dose administration of study drug.
- 16-Week Double-Blind Treatment Period (DBTP): Starts on the day of the first IMP administration and ends prior to the day of first IMP administration in the maintenance period (first IMP in the MP typically occurs at Week 16, but for those that miss the Week 16 IMP, first IMP in the MP will be the first IMP administration after Week 16). For study participants that withdraw from the study prior to start of IMP in the maintenance period, the DBTP ends on the day of the ET Visit.

See Section 3.7 (Treatment assignment and treatment groups) for allocation of AEs that occur on the day of IMP administration.

For vital sign parameters, the DBTP will start at the day and time of first IMP administration and ends prior to the day and the time of first IMP administration in the MP as there are 3 assessments collected at Baseline and Week 16 (one pre-dose, one 30 minutes post-dose and one 1-hour post-dose).

- 36-Week Maintenance Treatment Period (MP): Starts on the day of IMP administration at the Week 16 visit and ends 28 days (one dosing interval) after the day of last IMP administration before the Week 52 visit. For participants that do not receive IMP at the Week 16 visit, the MP starts on the day of first IMP administration after Week 16. For study participants that

withdraw from the study after Week 16 but before Week 52, the MP ends on the day of the ET Visit. In the event that no ET visit is performed, the MP ends 28 days after the last IMP administration.

For vital sign parameters, the day and the time will be used to define the MP for the same reason that given above.

- **Safety Follow-Up Period:** The SFU period will be defined for all study participants who complete the final IMP administration of the study at Week 48 and do not enter the OLE study, or for study participants who discontinue early including those withdrawn from IMP.
 - For study participants who complete the final IMP administration of the study at Week 48 and do not enter the OLE study, the SFU period starts 29 days after the day of last IMP administration before the Week 52 visit and ends on the day of the SFU Visit or on the last contact date, whichever happens later.
 - For study participants who discontinue early, the SFU period starts the day after the ET Visit and ends on the day of the SFU Visit or on the last contact date, whichever happens later. In the event that no ET visit is performed, the SFU period starts 29 days after the day of last IMP administration.

Per study protocol, if the Week 52 Visit or ET visit is done \geq 20 weeks after the final dose of IMP, the SFU Visit is not required. In that case, the last contact date (Week 52, ET or earlier if applicable) will be used as end of the SFU period.

Note that an IMP administration is said to be “final” when it refers to the very last IMP taken by the study participant in the study. Otherwise, the IMP administration is said to be “last” for a specific study period.

Safety analyses will be summarized for the DBTP, MP, and Overall Periods. Summaries for the MP will also include the SFU period for study participants that do not enter the OLE or discontinue early in the MP. The SFU period for study participants that discontinue in the DBTP will only be summarized in the Overall Period tables.

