The Double-Blind Treatment Period ends after Week 16 assessments. At Week 16, study participants will transition from the double-blind, placebo-controlled treatment into the 36-week Maintenance Period. Study participants receiving placebo during the Double-Blind Treatment Period will be re-allocated to bimekizumab treatment at Week 16 after all study assessments have been completed.

From Week 20 onwards, all study participants will be eligible for nonbiologic rescue therapy.

[figure not shown]
Prior to the completion of the Maintenance Period, Investigators should discuss treatment options with the study participant. Study participants who are not withdrawn from IMP and who meet the eligibility criteria will be given the opportunity to enter an extension study to continue to receive bimekizumab.

Study participants discontinuing IMP during the Double-Blind Treatment Period or during the Maintenance Period will be encouraged to return for all scheduled visits through Week 52 and the SFU Visit, as applicable.

A schematic representation of the study design is presented in [Figure 2–1](#).

This document cannot be used to support any marketing authorization application and/or variations thereof.

Figure 2-1: Study design

Refer to the study clinical protocol for more detailed information on the study assessments and schedule of procedures.

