For study participants randomized to placebo that switched to bimekizumab at the Week 16 visit the laboratory data (only for the shift table analyses, the analyses on TEMA and Hy's Law cases) and the vital sign data (only for the TEMA analyses) will have an additional Baseline for the Maintenance Period that will correspond to the latest measurement on or prior to the first bimekizumab dose in that period. This Baseline will be called "Baseline Week 16". To avoid any confusion in the outputs where both Baseline values will be used, the Baseline relative to the administration of first study medication will be called "Baseline Day 1".

For the MRI substudy, Baseline will also be defined as the latest measurement for that study participant up to and including the day of administration of first study medication. However, the efficacy analyses for the substudy will be performed using two sets of study participants based on the date of the Baseline MRI relative to first study medication administration: 1) all eligible substudy participants with an MRI any time prior to first study medication administration, and 2) eligible substudy participants with an MRI performed any time from 3 weeks prior to the first administration of study medication up to the day of administration of first study medication. Ideally, the Baseline MRI would be performed as close to the first administration of study medication as possible to allow accurate measurement of disease status at Baseline by SPARCC and ASpiMRI-a (Berlin modification) score. However, several factors including rescreening and cross-screening of participants, the COVID-19 pandemic, and other unforeseen issues resulted in several participant MRI scans that were >3 weeks prior to the first administration of study medication. Because there is no generally accepted window for the definition of Baseline for MRI endpoints, two sets of participants were identified to include: 1) all eligible substudy participants, and 2) only participants with MRI's performed close to the first study drug administration. The threshold of 3 weeks prior to the first study drug administration was selected after consultation with imaging experts.

For spine x-ray, the Baseline value may be based on an x-ray performed up to 6 months prior to first administration of study drug.

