Tables/graph on time to ASAS response	RS (DB-period only)	
 • Placebo • BKZ 160mg Q4W 	Yes, for all visits up to Week 16 for each participant	Yes, rerun of analyses provided for interim analysis 1
By-visit tables	RS	
 • Placebo • BKZ 160mg Q4W 	Yes, for all visits up to Week 24 for each participant	Yes, for all visits up to Week 52 for each participant
Safety Variables				
Tables of adverse events	SS (DB-period only)	
 • Placebo • BKZ 160mg Q4W 	Yes, for all visits up to Week 16 for each participant	No
	MS (MP only)	
 • BKZ 160mg Q4W Total 	No	Yes, from Week 16 up to Week 52 for each participant
	SS (Overall period)	
 • BKZ 160mg Q4W Total 	Yes, for all visits up to date of Week 24 visit of last planned participant	Yes, for all visits up to date of Week 52 visit of last planned participant
By-visit tables on laboratory or VS data	SS (Overall period)	
 • Placebo / BKZ 160mg Q4W • BKZ 160mg Q4W 	Yes, for all visits up to date of Week 24 visit of last planned participant	Yes, for all visits up to date of Week 52 visit of last planned participant

Variable	Analysis Sets (study period)	Treatment groups	Interim Analysis 1	Interim Analysis 2
Type of tables Shift table or table on TEMA for laboratory data or Hy's Law cases	SS (DB-period only)	
 Placebo BKZ 160mg Q4W 	Yes, for all visits up to Week 16 for each participant	No
	MS ^a (MP only)	
 BKZ 160mg Q4W Total 	No	Yes, from Week 16 up to Week 52
	SS ^a (Overall period)	
 BKZ 160mg Q4W Total 	Yes, for all visits up to date of Week 24 visit of last planned participant	Yes, for all visits up to date of Week 52 visit of last planned participant
Table on TEMA for VS data	SS (DB-period only)	
 Placebo BKZ 160mg Q4W 	Yes, for all visits up to Week 16 for each participant	No
	MS ^a (MP only)	
 BKZ 160mg Q4W Total 	No	Yes, from Week 16 up to Week 52 for each participant
	SS ^a (Overall period)	
 BKZ 160mg Q4W Total 	Yes, for all visits up to date of Week 24 visit of last planned participant	Yes, for all visits up to date of Week 52 visit of last planned participant

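### The day-based end of the double-blind safety period puts pre-dose Week 16 laboratory samples in the Maintenance Period, contradicting Section 2.3 and Table 4-3 and leaving placebo abnormalities first seen at Week 16 treatment-emergent in no period-based table

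*SAP*

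**What the plan says.** Section 3.2.2.1.1 (study periods for safety data) sets the general boundary by calendar day. The DBTP definition reads "Starts on the day of the first IMP administration and ends prior to the day of first IMP administration in the maintenance period". The MP, in turn, "Starts on the day of IMP administration at the Week 16 visit". Two data types are treated separately:

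- Vital signs are cut by day and time: their DBTP "ends prior to the day and the time of first IMP administration in the MP".
- Adverse events are referred to Section 3.7, which gives switch-day events to placebo apart from listed anaphylactic, hypersensitivity and injection-site events.

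Laboratory and eC-SSRS data have no separate rule.

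Elsewhere the SAP places Week 16 assessments before the switch. Section 2.3 ends the DBTP once the Week 16 assessments are done, and says placebo participants are "re-allocated to bimekizumab treatment at Week 16 after all study assessments have been completed". Table 4-3 gives the coverage of the double-blind laboratory shift, TEMA and Hy's Law tables, and of the eC-SSRS table, as "Yes, for all visits up to Week 16 for each participant".

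Section 3.3 gives switched placebo participants an "additional Baseline for the Maintenance Period that will correspond to the latest measurement on or prior to the first bimekizumab dose in that period". It is called Baseline Week 16 and is used in the shift, TEMA and Hy's Law analyses.

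**The concern.** The double-blind versions of the shift, TEMA and Hy's Law tables are the only versions that set placebo beside bimekizumab. Section 10.3 presents the MP and overall versions under the bimekizumab total column alone. If the period flag follows Section 3.2.2.1.1, these randomised tables lose the sample taken after the longest double-blind exposure. If it follows Section 2.3 or Table 4-3, they keep it. Two programmers working from the same SAP could produce different tables.

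The later tables then treat the arms differently. A bimekizumab participant's Week 16 abnormality is moved to the MP but still counted. A placebo participant's is moved and then becomes the reference value.

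**Working it through.** The SAP states no figure to reproduce. The check classifies one sample under each rule and follows it through the planned tables.

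**Step 1: which period.** First dose is on Day 1. The nominal Week 16 dosing day is 16 × 7 + 1 = Day 113. The general rule gives DBTP = Days 1 to 112 and MP from Day 113. A sample drawn on Day 113 before the dose is therefore MP. The ±3-day visit window (Days 110 to 116) changes nothing, because the cut follows the actual dosing day: dosing on Day d ends the DBTP on Day d − 1. A vital sign taken at the same moment would be DBTP.

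**Step 2: who is affected.** Everyone dosed on the day of the Week 16 sample. A participant who misses that dose has a DBTP running to the day before the next dose, and one who withdraws before maintenance dosing has a DBTP ending on the early termination day. Their Week 16 samples stay in the DBTP. Read literally, the double-blind tables would contain Week 16 samples only from participants not dosed that day.

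**Step 3: follow the sample, for participants dosed at Week 16.**

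| Table | Bimekizumab arm | Placebo arm |
|---|---|---|
| DBTP shift, TEMA, Hy's Law | absent | absent |
| MP and overall TEMA, Hy's Law | post-Baseline, counted | Baseline Week 16, not counted |
| MP and overall shift | post-Baseline grade | starting grade only |
| By-visit values and changes (overall, Baseline Day 1) | included | included |
| Worst post-Baseline CTCAE grade (overall, Baseline Day 1) | included if parameter listed | included if listed, mixed with later bimekizumab exposure |
| Listings, including Grade 3 or 4 results | included | included |

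Section 10.3 states the exclusion of Baseline values for the TEMA summary. For Hy's Law, it follows from the use of Baseline Week 16 in Sections 3.3 and 10.3.

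**Step 4: how far the worst-grade table covers the gap.** Tables 10-2 to 10-4 define markedly abnormal values for 7 + 5 + 5 = 17 parameters. The Section 10.3 list for the worst-grade table contains 14 of them. The other 17 − 14 = 3 are glucose, ALP and, as printed, ALT. The list names AST twice, so ALT is probably a misprint; correcting it would give 15 of 17. The table does not show Hy's Law combinations.

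**Step 5: eC-SSRS.** Baseline Week 16 applies only to specified laboratory and vital-sign analyses. If eC-SSRS is collected at Week 16, a placebo participant's pre-dose report on the dosing day falls in the MP and appears under BKZ 160mg Q4W Total in the MP eC-SSRS table.

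**The case against.** A reader might infer that placebo Week 16 abnormalities are counted nowhere, or that the only placebo-controlled laboratory tables are affected. The SAP does not support either. The by-visit table uses nominal visits and Baseline Day 1, so it shows the randomised arms side by side through Week 16 whatever the period flag. The worst-grade table also counts the placebo sample for the parameters it lists, and Grade 3 and 4 results are listed. Section 10.3 further plans a table of liver-test thresholds met at any time on treatment. Its period list does not name that table, so the table is not clearly subject to the cut.

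The strongest objection is that the loss is not settled, because Section 2.3 and Table 4-3 both put Week 16 in the DBTP. That stands: this is a contradiction, not an agreed rule that removes data. It does not make the plan safe, since Section 3.2.2.1.1 is the operative definition from which period flags are derived.

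The cut also applies to both arms of the double-blind tables alike. It loses information there and is not shown to bias that comparison; the asymmetry arises in the MP and overall tables.

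Nor does the SAP support a general claim that suicidality on placebo is credited to bimekizumab. The adverse-event tables of suicidal ideation and behaviour follow Section 3.7 and keep switch-day events with placebo. Only the MP eC-SSRS questionnaire table is exposed, and only if there is a Week 16 assessment.

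**Conclusion.** The point holds as an internal contradiction with a specific consequence. Under the literal period definition, pre-dose Week 16 laboratory samples of participants dosed that day drop out of the double-blind shift, TEMA and Hy's Law tables. For switched placebo participants, an abnormality first seen at Week 16 is then treatment-emergent in no period-based TEMA or Hy's Law table and enters the shift tables only as a starting grade.

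The reach is at most the planned 200 bimekizumab and 100 placebo participants, less those who stop early or miss the Week 16 dose. The number of abnormalities involved cannot be derived from the SAP.

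Two assumptions matter. First, a laboratory sample is taken at Week 16; the schedule is not shown, but Baseline Week 16 and Table 4-3 imply it. Second, the share of scheduled samples lost depends on that schedule. It would be 1 of 4 if sampling is every 4 weeks, or 1 of 6 if it follows the Week 1, 2, 4, 8, 12 and 16 visits that Section 8.3.3 names for CRP. Neither figure is established, and unscheduled values also enter the TEMA tables. The primary efficacy analysis is untouched.

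**What to change.** In Section 3.2.2.1.1, extend the vital-sign rule to laboratory and eC-SSRS data. Assessments made at the visit of first maintenance dosing and before that dose belong to the DBTP; those made after it belong to the MP. If the time is missing, treat Week 16 visit assessments as pre-dose. The default is useful for eC-SSRS, which Section 10.4.3 matches to visits by date.

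Keep the laboratory sample as Baseline Week 16 for switched placebo participants in the MP tables; it can be the last DBTP value and the MP reference at once. Leave the adverse-event rule in Section 3.7 as it is. PHQ-9 and ECG need no change, because they are summarised only for the overall period.

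This brings the period definition into line with Section 2.3 and Table 4-3. It uses the reasoning that Section 3.2.2.1.2 already applies to Week 16 efficacy data. The cost is one sentence and a change to the period flag in the analysis datasets, with no new data. It is best made before treatment codes are released for the Week 24 analysis, which is when the double-blind tables are produced.

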Unless stated otherwise, statistical tests of efficacy variables will be performed 2-sided and p-values will be rounded to 4 decimal places. P-values less than 0.0001 will be presented as “<0.0001” and p-values greater than 0.9999 will be presented as “>0.9999.” Statistical comparison will be performed at the 0.05 level of significance.

The SAS® outputs supportive of any inferential statistics that are part of the hierarchical testing procedure (ie, all inferential statistics associated with the endpoints in figure 4.1) will be provided as a separate PDF document in addition to TFLs. These outputs will be included in the ‘Documentation of Statistical Methods’ section of the clinical study report.

Unless specified differently in the SAP, the order of treatment groups to be presented in tables from left to right will be:

- Placebo
- Bimekizumab 160mg Q4W

Selected tables may include columns for:

- all study participants, regardless of study treatment
- all study participants on bimekizumab, regardless of whether they shifted from placebo after the Double-Blind Treatment Period or not
- study participants randomized on placebo who shifted to bimekizumab after the Double-Blind Treatment Period

The abbreviation for bimekizumab is BKZ and will be used in tables and listings headers. In the TFLs study participants on bimekizumab 160mg will be displayed as “BKZ 160mg Q4W”.

All study participants dosed with bimekizumab will be summarized in some TFLs in a treatment column labeled as “BKZ 160mg Q4W Total”.

For all TFLs not dedicated to the Double-Blind treatment period only, the Placebo-randomized study participants who shifted to bimekizumab after the Double-Blind Treatment Period will be summarized in a treatment column labeled as “Placebo / BKZ 160mg Q4W”.

Per protocol,

- visit windows of ± 3 days are permissible for all visits through Week 16 (included). The visit window is relative to the Baseline Visit.
- visit windows of ± 4 days are permissible for all visits after Week 16,
- for the SFU Visit, the visit should occur no more than 3 days prior to the scheduled visit date and within 7 days after the scheduled visit date.

Only data collected at the scheduled visit will be included in the analysis. The only deviations may concern PK data, unscheduled vendor data collected with a few days of delay, and MRI data (see below).

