6.4 Prior and concomitant medications

Prior medications include any medications that started prior to the start date of study medication.

Concomitant medications are medications taken at least one day in common with the study medication dosing period (defined as from first dose of study medication [including placebo] up to last dose of study medication + 28 days for the double-blind treatment period).

For study participants who discontinue early, the dosing period ends at the last study medication date + 28 days (one dosing interval). For study participants who complete the study as planned, the dosing period ends at the later of the following two dates:

- Last study medication date + 28 days
- The last scheduled visit date not including SFU

In the case of missing data, the classification of medications as prior or concomitant will be performed as described in Section 4.2.3. Imputations of missing data will be performed before calculation of relative study days.

The number and percentage of study participants in the SS taking prior medications will be summarized by treatment group, overall and by ATC class, presenting Anatomical Main Group (ATC Level 1), Therapeutic/Pharmacological Subgroup (ATC level 3), and PT. The table summary will be ordered alphabetically for the Anatomical Main Group and in terms of decreasing frequency for PT within Anatomical Main Group in the bimekizumab treatment group. In the event of ties, PT will be ordered alphabetically.

The number and percentage of study participants taking concomitant medications will be summarized similarly in a separate table. The summary will be presented on the SS for the Double-Blind Treatment period, as well as on the MS for the Maintenance Treatment Period.

In addition, separate summary tables for concomitant NSAIDs and for selected concomitant medications will be created for each treatment period

A by-study participant listing of all prior and concomitant medications as well as glossary of all medical medications will be provided on RS.

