10.1.2 Duration of exposure and time at risk in the Maintenance Period

- The study medication duration during the Maintenance Period will be calculated as follows:

$$\text{Date of last dose (MP)} - \text{Date of first dose (MP)} + 28$$

- If date of last dose in the Maintenance Period + 28 days extends to a date beyond the final visit date of the Maintenance Period (not including SFU), then this calculation reverts to:

$$\text{Date of last visit (MP - not including SFU)} - \text{Date of first dose (MP)} + 1$$

- For study participants who die during the Maintenance Period, then this calculation reverts to:

$$\text{Date of death} - \text{Date of first dose (MP)} + 1$$

- For study participants who discontinue/lost to follow-up during the Maintenance Period, then this calculation reverts to:

$$\text{Date of last dose (MP)} - \text{Date of first dose (MP)} + 28$$

- The time at risk during the Maintenance Period will be calculated as follows:

- For study participants who complete the Maintenance Period as planned and continue into an open-label study (and, therefore, do not have the SFU visit in the feeder study):

$$\text{Date of last visit (MP)} - \text{Date of first dose (MP)} + 1$$

- For study participants who die during the Maintenance Period, then this calculation reverts to:

$$\text{Date of death} - \text{Date of first dose (MP)} + 1$$

- For all other study participants, use the minimum of the following:

- $$\text{Date of last dose (MP)} - \text{Date of first dose (MP)} + 140 + 1$$
 - $$\text{Date of last clinical contact} - \text{Date of first dose (MP)} + 1$$

This last group could include study participants who discontinue the Maintenance Period early, study participants who complete the Maintenance Period as scheduled but choose not to continue into an open-label study, or study participants who are ongoing in the SFU period at the time of the interim data snapshot.

Note that the Week 24 visit (ie, Visit 10) will be the last visit for the Week 24 interim analysis, and that the Week 52 visit (ie, Visit 17) will be the last visit for the Week 52 interim analysis.

10.1.3 Duration of exposure and time at risk in the combined Double-Blind Treatment and Maintenance Periods

- The study medication duration during the combined treatment period will be calculated as follows:

- For study participants who do not switch study treatments per study design:

$$\text{Date of last dose} - \text{Date of first dose} + 28$$

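### For completers who enter the extension, the safety Maintenance Period stops 28 days after the last dose with no period after it, while the Maintenance Period tables and time at risk run to Week 52

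*SAP*

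**What the plan says.** For a participant who does not withdraw before Week 52, SAP Section 3.2.2.1.1 states that the safety MP "ends 28 days (one dosing interval) after the day of last IMP administration before the Week 52 visit". The early-termination rules in the same section apply only to withdrawal between Week 16 and Week 52.

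The SFU period exists only for participants who finish dosing "at Week 48 and do not enter the OLE study, or for study participants who discontinue early including those withdrawn from IMP". For the non-OLE completers, "the SFU period starts 29 days after the day of last IMP administration before the Week 52 visit", so it follows the MP without a break. Section 3.2.2.1.1 also includes their SFU data in the MP summaries. A completer who enters the OLE has no SFU period.

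Section 3.1 states that "visit windows of ± 4 days are permissible for all visits after Week 16".

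Other parts of the SAP run to Week 52:
- Section 3.2.1.2 ends the Treatment Period at the Week 52 visit for completers.
- Table 4-3 (Section 4.3.1) gives the coverage of the MP tables for adverse events, markedly abnormal (TEMA) vital signs and eC-SSRS as "Yes, from Week 16 up to Week 52 for each participant". Its row for laboratory shifts, TEMA values and Hy's Law cases also runs from Week 16 to Week 52.
- Section 10.1.2, for those who "complete the Maintenance Period as planned and continue into an open-label study", sets MP time at risk to the date of the last MP visit minus the date of the first MP dose, plus 1.

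**The concern.** The same participant has two different ends to the MP. Section 3.2.2.1.1 decides which events and values are classified as MP. Section 10.1.2 decides how many days go into the exposure-adjusted rates. When the Week 52 visit falls later than day 28, the second end is later than the first, and for an OLE entrant no other safety period in Section 3.2.2.1.1 covers the days between.

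Two things follow from the literal text. First, an adverse event, markedly abnormal value, shift, Hy's Law case or eC-SSRS report dated at the Week 52 visit enters or misses the MP-only table according to where that visit fell within its permitted window. Second, the MP exposure-adjusted incidence and event rates count days in the denominator on which no event can be counted in the numerator. A programmer who follows Section 3.2.2.1.1 and one who follows Table 4-3 would flag the same Week 52 record differently.

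**Working it through.** **Inputs.** MP end = last dose + 28 days (Section 3.2.2.1.1). Window = ±4 days after Week 16 (Section 3.1). Time at risk for OLE entrants = last MP visit − first MP dose + 1 (Section 10.1.2). Nominal days are 7 × week: Week 16 = 112, Week 44 = 308, Week 48 = 336, Week 52 = 364.

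**The plan's own figure.** 364 − 336 = 28 days. From Week 16 to Week 48 + 28 days is 224 + 28 = 252 days = 36 weeks. On nominal dates the Week 52 visit falls exactly on the last MP day, and there is no gap.

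**With the permitted windows.** Interval from Week 48 dose to Week 52 visit = 28 + (d52 − d48), each d from −4 to +4.
- Range: 28 − 8 = 20 to 28 + 8 = 36 days, so the visit can be up to 36 − 28 = 8 days past the MP end.
- Dose exactly on Week 48: 24 to 32 days; 4 of the 9 permitted visit days are day 29 or later.
- All combinations: 9 × 9 = 81. The visit is later than day 28 in 36 (44%), on day 28 in 9, and before it in 36.
- Size of the overshoot: the sum of k(9 − k) for k = 1 to 8 is 120 days, so 120/36 = 3.3 days where there is a gap and 120/81 = 1.5 days averaged over all combinations.

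These counts give every pair of days equal weight. They illustrate the windows and do not estimate the proportion of participants.

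**Week 48 dose missed, last dose at Week 44.** 364 − 308 = 56 days, ±8 gives 48 to 64. Less 28, the uncovered interval is 20 to 36 days.

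**Numerator against denominator.** Take Week 16 dosed on time and the Week 52 visit at +4 days (day 368).
- Time at risk: 368 − 112 + 1 = 257 days.
- MP, Week 48 on time: (336 + 28) − 112 + 1 = 253 days. Difference 4 days, or 4/257 = 1.6%.
- MP, Week 48 at −4 days: (332 + 28) − 112 + 1 = 249 days. Difference 8 days, or 8/257 = 3.1%.

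**Assumption on the window.** Section 3.1 ties it to the Baseline Visit expressly only through Week 16; the calculation takes the same for later visits. If it were counted from the preceding visit, the interval would be 24 to 32 days and the largest gap 4 days.

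**The case against.** The strongest reply is that nothing is lost from reporting. Section 10.2 treats events up to 140 days after the final dose as treatment-emergent, and the adverse event, TEMA, shift, Hy's Law and eC-SSRS tables are all also produced for the Overall period. By-visit laboratory and vital-sign summaries use nominal visits over the Overall period. Section 10.3 excludes from the markedly abnormal laboratory table only Baseline values and values more than 140 days after the last dose. Table 4-3 shows that Week 52 was meant to be covered. The MP tables are descriptive, with a single bimekizumab column.

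All of this stands as a limit on the consequence. It does not settle which MP end applies: Section 3.2.2.1.1 makes the MP a formal reporting period, and its text and Table 4-3 give different answers for the same record.

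Three stronger readings are tempting and are not supported:
- That end-of-treatment safety data belong to no period at all. The gap days lie inside the Treatment Period of Section 3.2.1.2 and the events reach the Overall tables; what is missing is one of the safety periods listed in Section 3.2.2.1.1.
- That 44% of OLE entrants, or all of them, are affected. Only those with a Week 52 visit later than day 28 are, and the SAP gives neither the number entering the OLE nor the distribution of visit days.
- That Section 6.4 contradicts Section 3.2.2.1.1. There "the dosing period ends at the later of the following two dates", but that rule serves the classification of concomitant medications, a different purpose.

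**Conclusion.** The inconsistency is real and should be corrected, but its effect is small. For completers entering the OLE, Section 3.2.2.1.1 cannot be reconciled with Table 4-3 and Section 10.1.2 whenever Week 52 falls on day 29 or later, which permitted visit dates allow without any protocol deviation. The mismatch is up to 8 days per participant with an in-window Week 48 dose (about 3% of MP time at risk at worst), and 20 to 36 days after a missed Week 48 dose; the SAP gives no frequency for either.

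The effect is confined to MP-only summaries: events and values may be left out, and exposure-adjusted rates are then slightly understated. Overall tables and efficacy analyses are not touched. Non-OLE completers dosed at Week 48 have no gap. The conclusion rests on applying Section 3.2.2.1.1 as written, and the day counts rest on the window assumption stated in the check.

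**What to change.** In Section 3.2.2.1.1, add that for participants who complete treatment and enter the OLE the safety MP ends on the day of the Week 52 visit. This agrees with the time at risk in Section 10.1.2, the coverage in Table 4-3 and the Treatment Period end in Section 3.2.1.2. Leave the 28-day MP end and the day-29 SFU start unchanged for non-OLE completers dosed at Week 48.

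Taking the later of last dose + 28 days and the Week 52 visit, as Section 6.4 does, would close the gap but leave the reverse mismatch: when Week 52 falls before day 28 (also 36 of the 81 combinations), the MP would run up to 8 days past the point where time at risk stops.

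The cost is one sentence and a change to the period flag in the analysis datasets. No new data are needed.
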